1.1 Rationale for Conducting the Study

The purpose of this study is to obtain additional data on the efficacy, PK, immunogenicity, and safety of *wilate* in paediatric patients below the age of 6 years with severe VWD undergoing regular prophylaxis, thus supplementing the existing body of data to obtain approval of *wilate* in the prophylactic treatment of severe VWD in this patient population. Other studies have demonstrated a beneficial effect of prophylaxis with VWF treatment in patients with severe VWD, including paediatric patients. These reported reduced mucosal and joint bleeding rates; decreased median ABR, a reduced incidence of major bleeds, and good tolerability:

- Treatment of mucosal bleeding (epistaxis and gastrointestinal bleeding) and joint bleeding remains problematic in clinically severe VWD. Patients are often unresponsive to treatment (e.g. desmopressin or antifibrinolytic therapy) and may require VWF replacement therapy. A prospective, treatment escalation design study evaluated the effect of escalating dose prophylaxis in 11 patients with severe VWD (median age 34.6 years). Use of prophylaxis with VWF concentrates reduced mucosal and joint bleeding rates. The median ABR decreased from 25 to 6.1 (95% confidence interval [CI] of the rate difference: -51.6 to -1.7) [8].
- A recent phase 3, multi-centre, open-label trial included 17 previously treated children <12 years old with severe type 1, 2A, or 3 VWD (VWF:RCo <20% at screening or a documented history of VWF:RCo <10%), for whom DDAVP treatment had been ineffective, contraindicated, or unavailable. Participants received on-demand treatment of nonsurgical bleeds, were undergoing a surgical procedure, or were treated on a predefined prophylactic regimen with a plasma-derived VWF/FVIII concentrate. The duration of study participation ranged from 12 to 13 months. Pharmacokinetic parameters for VWF markers were generally comparable to adults but showed lower VWF:RCo exposure, as indicated by a lower incremental recovery, shorter half-life, and faster clearance. Incidence of major bleeds was lower for prophylaxis (3.3%) than on-demand therapy (27.1%); joint bleeds were also lower (3.3% vs 11.5%, respectively). Investigator-reported excellent/good haemostatic efficacy against nonsurgical bleeds was 100%. No clinically relevant differences in PK, haemostatic efficacy, or safety were observed between age groups (<6 years and 6 to <12 years). The treatment was well tolerated. Adverse events were mild to moderate and consistent with the adult safety profile. No cases of anaphylactic reactions or angioedema, development of FVIII/VWF inhibitors, thromboembolic events, or viral infections were reported [9].
- A study found that 23% (184/804) of VWD patients self-reported joint bleeds. These 184 patients reported joint damage more often (54% vs. 18%, $p<0.001$) and had lower health-related QoL (SF-36, $p<0.05$) compared to VWD patients not reporting joint bleeds. Of 55 patients with available joint bleed data, 65% had the first joint bleed in childhood. These 55 patients used more clotting factor concentrate ($p<0.001$), more often had X-ray joint damage (44% vs. 11%, $p=0.001$) and chronic joint pain (44% vs. 18%, $p=0.008$) compared to 55 control VWD patients without joint bleeds [10]. Therefore, it was considered valuable to measure the HJHS score in the enrolled paediatric patients, because although the HJHS score has been validated in adult patients [11], there are no validated tools to determine QoL or disease-specific tools to assess the musculoskeletal status in paediatric patients with severe VWD.

Since there are insufficient data on use of *wilate* in paediatric patients with severe VWD below the age of 6 years, Octapharma plans to evaluate the efficacy of *wilate* in bleeding prophylaxis in these patients.

1.2 Dose Rationale

Doses of *wilate* vary based on the indication. The doses for prophylaxis (30–50 IU/kg BW administered 2–3 times per week), the treatment of BEs, and perioperative prophylaxis are detailed in Section 5.2. Because there are currently insufficient data to recommend the use of *wilate* in children under 6 years of age, the dose rationale was based on recommended doses in adults and children over 6 years of age [12, 13], with some adjustments allowing for the fact that, contrary to adults, 1 IU/kg BW VWF:Ac and FVIII:C may not raise the plasma level by as much as 1.5–2% of normal activity for the respective proteins in children below the age of 6 years.

1.3 Benefit-Risk Statement

The following adverse drug reactions (ADRs) are known to occur with other VWF/FVIII preparations and may also occur with the use of *wilate* [7]:

- **Hypersensitivity or allergic reactions** (which may include angioedema, burning, and stinging at the infusion site, chills, flushing, generalised urticaria, headache, hives, hypotension, lethargy, nausea, restlessness, tachycardia, tightness of the chest, tingling, vomiting, wheezing) have been observed upon use of *wilate* and may, in some cases, progress to severe anaphylaxis (including shock) with or without fever. On rare occasions, fever has been observed.
- Patients with VWD, especially type 3 patients, may develop **neutralising antibodies (inhibitors) to VWF and/or FVIII**. If expected VWF:Ac and/or FVIII:C activity plasma levels are not attained or bleeding is not controlled with an appropriate dose, an appropriate assay should be performed to determine whether a VWF inhibitor and/or factor VIII inhibitor is present. In patients with high titres of inhibitor, VWF therapy may not be effective, and other therapeutic options should be considered.
- As for all medicinal products prepared from human blood or plasma, infectious diseases due to **transmission of infective agents** cannot be totally excluded. This also applies to pathogens of hitherto unknown origin. The manufacturing process of *wilate*, which includes two viral inactivation steps with different chemical/physical action principles, represents a high standard for plasma-derived concentrates in terms of pathogen safety. The measures taken are considered effective for enveloped viruses such as human immunodeficiency virus (HIV), hepatitis B virus (HBV) and hepatitis C virus (HCV), and for the non-enveloped hepatitis A virus. The measures taken may be of limited value against non-enveloped viruses such as parvovirus B19.
- **Thrombotic events**. When using a FVIII-containing VWF product, the treating physician should be aware that continued treatment may cause an excessive rise in FVIII:C. Patients receiving FVIII-containing VWF products should be monitored for sustained excessive FVIII:C plasma levels, which may increase the risk of thrombotic events. The risk of occurrence of thrombotic events in patients using FVIII-containing VWF products is

particularly increased in patients with known clinical or laboratory risk factors. Therefore, patients at risk must be monitored for early signs of thrombosis. Prophylaxis against venous thromboembolism should be instituted in accordance with current recommendations.

In view of its state-of-the-art manufacturing process and available clinical and post-marketing evidence, the benefit-risk evaluation of *wilate* is positive, including paediatric patients.

1.4 COVID-19 Benefit-Risk Statement

For the WIL-33 study, patients and their parents are required to come into the treatment centre for 8 visits over a period of approximately 12 months in order to participate in the study. There is therefore a risk that the parents may become exposed to COVID-19 and potentially even infected. The standard safety measures will be in place at the treatment centres in line with the local requirements.

Potential COVID-19 related risks for site management and project management will be evaluated in advance and options such as alternative monitoring approaches will be implemented. In addition, for the support of the study processes (e.g. provision of the study medication and transport of the blood samples), only well-established service providers are selected which have strong regional expertise and strict risk and quality guidelines in place, including with regards to potential COVID-19-related risks. The current regulations regarding transport and logistics will be continuously monitored for the countries participating in the study, and flexible solutions and longer lead times will be implemented wherever appropriate. In order to address the risk of delays in study visits, exceeding the permitted time windows for visits on grounds of COVID-19-infection on the part of patients/parents or study staff at the sites is excluded from classification as major protocol deviation in all cases. Also, the number of patients as required by the EU guideline CPMP/BPWG/2220/02 [15], which requires at least 8 patients with severe VWD under the age of 6 years, has been increased by 150% to 12 patients, not least to counteract possible COVID-19-related drop-outs.

The potential impact of COVID-19 on the patients, the patient's parents and the study performance was weighed up against the negative impact of not doing the study, i.e. that *wilate* treatment will not be adequately assessed for use in paediatric patients. Overall, the benefit-risk evaluation of *wilate* and of performing this study is positive.

2 STUDY OBJECTIVES

2.1 Primary Objective(s)

The primary objective of this study is to determine the efficacy of *wilate* in the prophylactic treatment of up to 12 paediatric patients (eight evaluable) with severe VWD (defined as screening von Willebrand factor ristocetin cofactor activity [VWF:RCo] <20%) under the age of 6 years, for a period of 12 months.

2.2 Secondary Objective(s)

The secondary objectives of this study are to:

- Determine the pharmacokinetics (PK) of *wilate* for VWF:Ac (VWF:RCo) and FVIII:C (one-stage [OS])
- Determine incremental in-vivo recovery (IVR) of *wilate* over time
- Evaluate the rate of traumatic and spontaneous breakthrough bleeds under prophylactic treatment, including the corresponding treatment efficacy
- Assess the treatment response in minor and major bleeds and surgeries
- Determine *wilate* consumption data for prophylactic treatment, on-demand treatment, and surgeries
- Investigate the immunogenic potential of *wilate* by screening for VWF and FVIII inhibitors
- Investigate the thrombogenic potential of *wilate*
- Assess the patients' joint status with the Haemophilia Joint Health Score (HJHS)
- Assess the safety and tolerability of *wilate*

2.3 Exploratory Objective(s)

The exploratory objective of this study is to investigate the VWF multimer composition in the hereditary type 3 VWD paediatric patient group.

3 INVESTIGATIONAL PLAN

3.1 Primary and Secondary Endpoints

3.1.1 Primary Endpoint

The primary endpoint of this study is to determine the total annualised bleeding rate (tABR) during prophylactic treatment with *wilate*.

3.1.2 Secondary Endpoints

The secondary endpoints of this study are to determine:

- PK profile characteristics of VWF:Ac (VWF:RCo) and FVIII:C (OS) based on blood samples taken pre-dose (baseline), 15 minutes, 3, 9, 24, 48 and 72 hours after dosing of 80 IU/kg BW *wilate*
- Incremental in-vivo recovery (IVR) of *wilate* for VWF:Ac (VWF:RCo) and FVIII:C (OS) over time (at baseline and at 1, 2, 3, 6, 9, and 12 months of treatment)
- Efficacy of *wilate* in the prevention and treatment of spontaneous and traumatic breakthrough BEs based on their rate the proportion of spontaneous and traumatic BEs successfully treated with *wilate* as assessed by the use of a 4-point ordinal haemostatic efficacy scale (excellent – good – moderate – none), respectively
- The overall efficacy of *wilate* in perioperative prophylaxis against excessive bleeding as assessed at the end of the postoperative period by the responsible treating Investigator. A 4-point ordinal haemostatic efficacy scale (excellent – good – moderate – none) will be used
- *wilate* consumption data for prophylactic treatment, for on-demand treatment and during surgical prophylaxis

3.1.3 Safety Parameters

Secondary Endpoints

- Incidence of VWF and FVIII inhibitors
- Incidence of thromboembolic events
- Joint Health Status determination by the use of the HJHS, given the patient's age and constitutional development allow this assessment
- Safety and tolerability of *wilate* assessed by monitoring AEs throughout the study

3.1.4 Exploratory Endpoint

The exploratory endpoint of this study, which is solely investigated in the hereditary type 3 VWD patient group with ≥ 14.5 kg body weight, is a VWF multimer analysis from the PK samples taken at 15 minutes, and 24 hours after *wilate* injection, by using multimer analysis using low- and high resolution electrophoresis gels.

3.2 Overall Study Design and Plan

This is an open, prospective, non-controlled, international, multi-centre phase 3 study investigating the efficacy, pharmacokinetics, immunogenicity, and safety of *wilate* in paediatric

patients below the age of 6 years at the time of screening with severe VWD (defined as VWF:RCo <20%, regardless of prior treatment) undergoing regular prophylaxis. The study is estimated to start in Q3 2021 and to be completed by Q2 2024 resulting in an overall duration of 2 years and 6 months.

"Regardless of prior treatment" in this context means that both subjects previously treated with VWF/FVIII-containing products (either on-demand treatment or regular prophylactic treatment) and previously untreated patients (PUPs) can be included in the study.

Overall, 12 patients (eight evaluable) will be enrolled by up to 15 sites worldwide. At least four of these patients should be suffering from hereditary type 3 VWD. The remaining patients can be diagnosed with severe type 2 (except 2N) or severe type 1 VWD.

Of the 12 patients, at least eight patients should be evaluable for the primary endpoint.

The planned prophylactic treatment duration per patient is 12 months.

Patients will participate in the following visits: Screening Visit, PK Visit, 1-Month, 2-Month, 3-Month, 6-Month, and 9-Month Visits, and a Study Completion (12-Month) Visit. Moreover, "Compliance Calls" will be performed every 5–7 weeks after the 3-monthly IVR visits at 3, 6, and 9 months (detailed in **Section 6.1** and in the flow chart of assessments by study visit [**Table 1**]).

The start of the prophylactic treatment phase is defined as the first IMP injection after collection of the last PK sample (i.e. the 72-hour sample), which is administered at the study site before patients return to home treatment. Parents will receive product for home treatment and will be instructed on proper storage and administration. Involvement of a physician or a study nurse will be documented.

Where needed, external home-care companies with experience in conducting clinical trials will be contracted, with trained nurses supporting patients' parents by providing training, re-training, and oversight through home-care visit support throughout the study or as needed.

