3.3 Discussion of Study Design and Choice of Control Group(s)

3.3.1 Study Design

This open-label, prospective, non-controlled, international, multi-centre phase 3 study is designed to evaluate the efficacy of *wilate* in bleeding prophylaxis in paediatric patients below 6 years of age with severe VWD.

There is currently no data available on the tABR of patients <6 years of age with VWD undergoing regular prophylaxis. Description of the effect of prophylaxis on the tABR of patients with inherited coagulation disorders has been used as an efficacy endpoint to evaluate the clinical benefit of this intervention.

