9.2.2.1 Efficacy of *wilate* in Prophylactic Treatment

The haemostatic efficacy of *wilate* will be assessed by evaluating tABR over all types of VWD.

The frequency and severity of BEs and the total, traumatic and spontaneous ABR will be calculated from patients' dosing and treatment frequency in different VWD types. Efficacy of prophylactic treatment with *wilate* will be statistically evaluated by analysing the primary endpoint.

The tABR will be calculated as the total number of spontaneous bleeds, traumatic bleeds, and other bleeds occurring in the time period between first prophylactic dose of *wilate* and the Study Completion Visit, divided by the duration (in years) between first prophylactic dose of *wilate* and the Study Completion Visit. Bleeding episodes occurring within surgery periods will be excluded from the calculation of tABR.

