3.8 Subgroup analyses

As mentioned in section 1.3 of the SAP, an additional multimer analysis using low- and high-resolution electrophoresis gels will be performed only in the subgroup of patients with hereditary type 3 VWD with ≥ 14.5 kg body weight. The multimer composition will be investigated over time for PK sampling time points 15 minutes, and 24 hours after IMP injection (for details see section 4.7.3).

The analysis of demographics and all efficacy analyses (except for the VWF type 3 subgroup) will be stratified by the following subgroups:

- VWD type ('severe type 1', 'type 2' and 'type 3')
- Sex ('Female', 'Male')

The safety analysis will be stratified by sex.

Statistical Analysis Plan	Version 2.0		Page 10 of 27
Sponsor	Octapharma	Protocol No	WIL-33

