4.7.3 Exploratory endpoints

Multimer analysis

The exploratory endpoint of this study, which is solely investigated in the hereditary type 3 VWD patients with ≥ 14.5 kg body weight, is a VWF multimer analysis from the PK samples taken at 15 minutes, and 24 hours after IMP injection, by using multimer analysis using low- and high-resolution electrophoresis gels. In addition, the VWF multimer analysis is performed at baseline in all patients.

The multimeric pattern for each sample will be assessed at an independent laboratory. Gels were run at concentrations of 1.2% (low resolution gel) and 1.6% (medium resolution gel), a normal plasma pool sample served as control

Data from the densitometry readings of the gel will be presented as percentage of the multimer bands relative to the total bands. In the 1.2% gels three groups (bins) of multimer peaks will be analyzed, small multimers (bands 1-5), intermediate multimers (bands 6-10) and large multimers (bands > 10) and a narrative description will be provided in addition. For the 1.6% gels, only the triplets narrative description will be provided in line with the reports of the central laboratory. The frequency distribution of standardized narrative descriptions will be displayed for both, the 1.2% and 1.6% gels.

For the screening samples, descriptive statistics of the three multimer groups/bins will be presented per VWD type and sex and for the corresponding plasma pool values.

In VWD type 3 patients, descriptive statistics of the multimer groups will be analysed in addition by time point (i.e. 15 minutes and 24 hours post infusion) including analysis of changes with time (24 hours vs. 15 minutes) as well as in comparison with a normal plasma pool and frequency distribution of standardized narrative description. All individual multimer data will be additionally listed.

Statistical Analysis Plan	Version 2.0		Page 17 of 27
Sponsor	Octapharma	Protocol No	WIL-33

Annualized bleeding rates for treated bleedings

All of the analysis described for the primary end point including robustness analysis (see section 4.7.1) will be repeated for treated bleeds only.

Prior annualized total bleeding rates (pTABR)

The historical total number of bleeding episodes under On-Demand treatment/6 month and under prophylactic treatment/ ≤ 6 month collected at screening will be used to extrapolate the prior TABR (pTABR_{OD} and pTABR_{PROPH}) if a sufficient amount of data are available. This analysis will be purely descriptive.

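### The pooled primary tABR cannot by itself show whether bleeding changed; the SAP's separate prior rates need a within-child comparison and a split by prior regimen

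*Protocol*

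**What the plan says.** Entry is open to children with any treatment history: "both subjects previously treated with VWF/FVIII-containing products (either on-demand treatment or regular prophylactic treatment) and previously untreated patients (PUPs) can be included" (Protocol 3.2, repeated in 4.1). No quota by prior regimen is set.

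The primary endpoint reads "The primary endpoint of this study is to determine the total annualised bleeding rate (tABR) during prophylactic treatment with" *wilate* (Protocol 3.1.1). Protocol 9.2.2.1 adds that haemostatic efficacy "will be assessed by evaluating tABR over all types of VWD". Protocol 3.3.2 gives no control group, and Protocol 3.3.1 concedes: "There is currently no data available on the tABR of patients <6 years of age with VWD undergoing regular prophylaxis".

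SAP 3.8 says that demographic and efficacy analyses "will be stratified by the following subgroups", and then names VWD type and sex. Prior regimen is not among them, and SAP 4.5 only lists prior medication.

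SAP 4.7.3 does use history. Bleed counts collected at screening "will be used to extrapolate the prior TABR", separately for on-demand treatment (pTABR_OD) and prophylaxis (pTABR_PROPH). This analysis is exploratory, descriptive only, and done only if there are enough data. SAP 6.1 gives a formula for each rate but none for previously untreated children.

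**The concern.** The primary objective is the efficacy of prophylaxis. With no control and no outside rate, the natural reference is each child's own earlier bleeding. That reference means different things in the three groups. A child coming from on-demand treatment may improve, a child already on prophylaxis may simply stay controlled, and a previously untreated child has no treated history. A low pooled tABR could therefore reflect a fall in bleeding, continued control, or a mixture.

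The data to separate these readings are collected, but the planned summaries do not join them. pTABR_OD comes only from children with on-demand history, whereas the on-study tABR comes from everyone. A reader who sets one against the other compares different children. At stake is whether the report supports a correct statement about change in bleeding or invites a wrong one.

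**Working it through.** The plan gives no figure for a change in bleeding, so there is none to reproduce. The check has four steps.

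**1. What the primary endpoint contains.** SAP 6.1 defines TABR = bleeds in the prophylactic phase / (days in that phase / 365.25). No prior rate enters, so the result is the same whatever the children's rates were before.

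**2. Size of the error from an unpaired reading.** All rates here are assumptions. On-demand children fall from 25 to 10 per year, and prophylaxis children stay at 2. The 25 is the starting median of an escalation study cited in Protocol 1.1 (median age 34.6 years) and serves only as illustration. With k of 8 children from on-demand treatment:

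- pooled on-study tABR = (10k + 2(8 − k)) / 8
- apparent fall = 1 − pooled tABR / 25
- true within-child fall = (25 − 10) / 25 = 60% in on-demand children and 0% in prophylaxis children, at every k

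| On demand (of 8) | Pooled on-study tABR | Apparent fall against pTABR_OD |
|---|---|---|
| 2 | (20 + 12)/8 = 4.0 | 84% |
| 4 | (40 + 8)/8 = 6.0 | 76% |
| 6 | (60 + 4)/8 = 8.0 | 68% |
| 8 | 80/8 = 10.0 | 60% |

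The apparent fall depends on the enrolment mix. If the prophylaxis children bled more on study than the on-demand children, the error would run the other way.

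**3. The prior-prophylaxis rate.** SAP 4.7.3 describes the count as covering at most 6 months. SAP 6.1 divides by the whole time from the switch to prophylaxis until screening, and requires at least 4 months. If the count covers only the last 6 months, 3 bleeds give:

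- 6 months on prophylaxis: 3 / 0.5 = 6.0 per year
- 12 months: 3 / 1 = 3.0 per year
- 24 months: 3 / 2 = 1.5 per year

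A child who in fact bleeds at 6.0 per year before and during the study, with 24 months of earlier prophylaxis, would show a ratio of 6.0 / 1.5 = 4. That is an apparent fourfold rise. If the count covers the whole phase, the formula is sound, but the description in 4.7.3 is not.

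**4. What a paired comparison can bear.** Exact Poisson 95% intervals for one child's 6-month history:

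- 12 bleeds: 24 per year (12.4 to 41.9)
- 3 bleeds: 6 per year (1.2 to 17.5)

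If all n children improve, the smallest two-sided sign-test p is 2 × 0.5^n: 0.0078 for n = 8 and 0.125 for n = 4. Estimates and individual values are therefore appropriate, and a test is not.

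**The case against.** The strongest defence is that the study is openly descriptive. The endpoint is the rate on prophylaxis, the sample size comes from a guideline and an FDA communication, and no claim of reduction is planned in the text available. This stands as a reason not to ask for a control arm or a test. It does not answer a request for a descriptive table that pairs data already held.

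Four stronger readings are tempting, and the documents do not support them.

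- A reader might infer that the plan has no analysis by prior regimen. It has two regimen-specific prior rates, which permit an informal before-and-after reading. SAP 4.7.1 was not available for this review and the table list is a separate document, so a paired analysis there cannot be excluded.
- A reader might take the cited study ("The median ABR decreased from 25 to 6.1") and conclude that one pooled tABR of 6.1 fits any effect from 0% to 76%, since (25 − 6.1)/25 = 76%. Those ends follow from fixing the on-study rate at 6.1 and choosing the prior rates. No change from earlier prophylaxis is also not the same as no effect of prophylaxis.
- A reader might conclude that the trial cannot answer its efficacy question. The limit applies to the primary tABR taken alone. The concern about enrolling children who bleed little is also partly met, because inclusion criterion 2 requires severe VWD in need of replacement therapy.
- A reader might prefer the planned treated-bleed rate as the match to history. SAP 4.7.3 describes the history as a total count of episodes, and setting treated bleeds alone against it could create an apparent reduction.

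**Conclusion.** The concern holds in a limited form. The primary tABR pools three treatment histories without a control or an age-specific reference, so on its own it cannot show whether bleeding changed. The SAP's prior rates partly fill the gap, but the available text neither pairs them with the same child's on-study rate nor splits the on-study rate by prior regimen.

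Under the assumed rates, reading the on-demand prior rate against the pooled rate gives an apparent fall of 60% to 84%, depending on the mix, where the on-demand children's true fall is 60% throughout. These sizes are illustrative, because the documents give no rates for this age group. The count-window mismatch can change a prior-prophylaxis rate fourfold (6.0 against 1.5 per year), if the count covers 6 months and prophylaxis lasted 24. The conclusion about missing analyses is subject to what SAP 4.7.1 contains.

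**What to change.** 1. Reconcile SAP 4.7.3 with 6.1 so that the prior-prophylaxis count and its denominator cover the same period.
2. Add prior regimen at screening (on-demand, prophylaxis, previously untreated) to SAP 3.8 for the tABR tables.
3. In SAP 4.7.3, report each child's on-study tABR beside that child's own prior rate. Give the within-child difference, and the ratio where the prior rate is above zero, with individual values and descriptive summaries by prior regimen. Use the all-bleed tABR against the historical total count.
4. State how children without a usable prior rate are shown: previously untreated children, and those with under 4 months of prior prophylaxis. State which rate applies if a child has both.
5. Rest any statement of reduced bleeding on the prior on-demand children only.

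The cost is SAP wording, one table and one listing, from data that the SAP says are collected at screening. The downside is strata of a few children, possibly none in one of them, and a short historical period, so the comparison stays descriptive.
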